2. INTRODUCTION

Multiple sclerosis (MS) is a chronic immune-mediated inflammatory and neurodegenerative disease that affects central nervous system. Magnetic resonance imaging (MRI) is the main paraclinical examination used to monitor disease activity and response to treatment. However, there is only limited correlation between the clinical symptoms and findings seen on the conventional MRI – a phenomena called clinical-radiological paradox. Measuring whole and regional brain atrophy provides additional information to MRI and seems to correlate better with clinical course and prognosis. In the last two decades, brain atrophy in MS has been extensively studied, cut-offs for brain volume loss over time has been established and it is likely that it will become an important outcome measure in both clinical studies and routine practice.

Compared to brain atrophy, spinal cord (SC) atrophy and its relation to MS-related disability has been given less attention. This is partly due to technical challenges such as inhomogeneous magnetic field in this region, small physical dimensions of SC and artefacts caused by motion of the SC within the spinal canal together with the flow of cerebrospinal fluid and periodic motion due to respiratory and cardiac cycles. Moreover, focal spinal cord MS lesions may cause both swelling and shrinking of SC that influence its absolute volume, resulting in problems with interpretation of absolute SC volume in MS. Despite all these challenges, it is possible to identify SC lesions and reliably measure SC volume, but there is no „gold standard“ (standardized) software for SC volume measurement and no agreement on the SC level (segments) that is most suitable for SC volume loss measurement.

During 2016 we have developed an in-house semiautomatic pipeline for measurement of cervical spinal cord volume that is a part of Scanview program. The segmentation is performed on T2-weighted images. In the first step, a marker is manually placed in a center of an intervertebral disc C3-4 (sagittal plane). Subsequently a cord straightening (manual rotation of the cord to achieve a perpendicular orientation of spinal cord to dorsal part of C3 vertebral body), that enable to reduce partial volume due to the cord orientation. After this centering and straightening, transformation matrix is saved and all subsequent steps are fully automatized. These steps include: 1. Sub-pixel division, 2. Reversing the contrast of T2-weighted images and smoothing by applying a set of median, Gaussian and edge-enhancing filters and 4. Cubic spline interpolation to find a curve that represents a border of a spinal cord with highest probability. Finally, a sum of mean areas of 21 1-mm slices is calculated (1 center slice fixed at center of a intervertebral disc C3-4 and 2 x 10 slices in cranial and caudal direction).

Using this new software we have assessed 1,036 MS patients during 2016 and 2017. The intra- and inter-rater variability of SC volume assessment was done by using the intraclass correlation coefficient (ICC) with a two-way mixed absolute agreement and single-measures design. The analysis confirmed very good consistency (> 98%) of the method. The preliminary

results showed a significant correlation between spinal cord volume and different clinical phenotypes.

2.1. Study Rationale

To be able reliably evaluate spinal cord volume and its changes in MS patients we need to understand variability of these parameters in sex and age matched healthy controls. To date, no generally available data about these parameters in healthy controls are available. In addition, the result are scanner specific and using particular scanner we need to get these physiologic ranges particularly for the type of scanner where MS patients are evaluated.

The objective of this study is to investigate age and sex matched healthy controls by MRI to get the basic set of the data representing both cross sectional values and its longitudinal changes.

The present study will also investigate different strategies how to normalize the absolute spinal cord and brain volume data, what is a relationship between spinal cord volume and brain volume data and what is the best protocol to be used in a routine clinical practice

STUDY OBJECTIVES AND ENDPOINTS

2.2. Objectives

2.2.1. Primary Objective

The primary objective of the study is to longitudinally examine 102 healthy controls (HC) on MRI to get data about spinal cord volume. This data will be used to compare spinal cord volume in HC with spinal cord volume of age and sex matched multiple sclerosis (MS) patients.

2.2.2. Secondary Objectives

The secondary objectives of this study are as follows:

- Test several normalization strategies and choose the best variable or set of variables to normalize spinal cord volume
- Determine inter-subject variability in spinal cord volume in healthy subjects
- Determine inter-subject variability in different whole and regional brain volumes in healthy controls

2.2.3 Tertiary objectives

- Determine relationship between spinal cord volume and different whole and regional brain volumes.
- Optimize MRI protocol (different sequences) for separation of white and gray matter in cervical spine cord.

2.3. Endpoints

2.3.1. Primary Endpoint

Establishing pathological cut-offs for spinal cord volume able to discriminate with the highest sensitivity and specificity HC from MS patients. The analysis will be done both cross-sectionally and longitudinally.

2.3.2. Secondary Endpoints

- Description of results of different normalisation strategies, using different variables, e.g. sex, age, body height of HC, height of C3 vertebra (or other vertebra derivate metrics).
- Description of absolute and normalised spinal cord volume and its variability in predefined spinal segments in different age and sex groups of HC.
- Description of absolute and normalised brain volumes in HC measuring whole brain (total intracranial volume TIV) and different regional brain volumes, especially – gray and white matter compartment, corpus callosum, thalamus, and cerebellum.

2.3.3. Tertiary Endpoints

- Correlation between spinal cord volume (total and GM, WM separately) and several brain metrics (total brain volume, GM, WM, lateral ventricles, thalamus, corpus callosum, brainstem and cerebellum) in HC.
- Description of results from different MRI protocols (shorter and longer version, different sequences)

3. STUDY DESIGN

3.1. Study Overview

This is a prospective, longitudinal, monocentric, interventional study to examine 102 healthy subjects with MRI.

3.2. Overall Study Duration and Follow-Up

The study period will be overall 4 years. During first 12 months we plan to enroll 102 HC. The enrollment period will take maximum 12 months. The study duration for a particular subject will be 3 years. During this period each participant will be examined by MRI at month 0, 12, 24, and 36.

3.2.1. Enrollment of participants

Healthy controls suitable for this study will be offered to participate in this study based on personal discussion. During this meeting a participant will receive all important information about the study and all inclusion and exclusion criteria will be checked. After signing informed consent form the basic clinical evaluation will be done and the first MRI will be scheduled. The study is planned for 3 years for an individual person. Participant will be contacted always 2-4 months before the next MRI. At this time all important conditions will be checked again.

3.2.2. MRI Assessment

All participants will be examined on the same 3T scanner, Siemens Skyra, 20 channel coil for head and spinal cord. The same standardised protocol will be used - T2WI (weighted images) fat sat (FS) 3D for spinal cord volumetry, inversion recovery (IR) sequence for gray and white matter separation of spinal cord and T1 MPRAGE 3D sequence for brain volumetry.

Each participant will be examined by MRI at month 0, 12, 24, and 36.

3.3. End of Study

The end of study will be after completion of MRI assessment for all available participants, but no longer than 4 years from the first participant date of enrollment.

4. STUDY POPULATION

4.1. Inclusion Criteria

To be eligible to participate in this study, subject must fulfil the following eligibility criteria:

1. Each participant must provide informed consent in accordance with local regulations
2. Age 18-60 years.

4.2. Exclusion Criteria

Participant will be excluded from contributing to this study if any of the following exclusion criteria exist:

1. Not able to undergo MRI examination
2. Not able to be examined 4 times, i.e. M 0, 12, 24, 36 during the next 3 years
3. Pregnancy at the time of enrollment into the study
4. Other disease or medical condition that can influence the volume of brain or spinal cord

5. ASSESSMENTS

5.1. Prospective Acquisition of Demographics, Baseline and Follow-up clinical Characteristics, and Clinical Measures at month 0, 12, 24, and 36

- Age
- Sex
- Body weight and height at time of each MRI examination
- Regular check of medical history and changes in physical status
- Regular evaluation of adverse events including non-serious
- Neuropsychological testing
- Walking test (T25-foot walk test)

5.2. MRI Assessments at month 0, 12, 24, and 36

- Regular control of contraindication to MRI before any assessment
- Scan acquisition time
- Spinal cord volume (measured in a predefined cervical spinal cord segment in C3-C4 vertebral body)
- Antero-posterior width (APW) and transversal (or left-right) width (LRW) of spinal cord at the level of C3/C4 intervertebral disc
- Total intracranial volume
- Brain Parenchymal Fraction (BPF)
- Brain volume
- White matter (WM) volume
- Gray matter (GM) volume
- Deep gray matter volume (volume of basal ganglia, thalamus)
- Cerebellar volume
- Volume of brainstem
- Ventricular volume

6. STATISTICAL METHODS AND DETERMINATION OF SAMPLE SIZE

6.1. Endpoints

6.1.1. Primary Endpoint

Establishing pathological cut-offs for spinal cord volume able to discriminate with the highest sensitivity and specificity HC from MS patients. The analysis will be done both cross-sectionally and longitudinally.

6.1.2. Secondary Endpoints

- Description of results of different normalisation strategies, using different variables, e.g. sex, age, body height of HC, height of C3 vertebra (or others vertebra derivate metrics).
- Description of absolute and normalised spinal cord volume and its variability in predefined spinal segments in different age and sex groups of HC.
- Description of absolute and normalised brain volumes in HC measuring whole brain (total intracranial volume TIV) and different regional brain volumes, especially – gray and white matter compartment, corpus callosum, thalamus, and cerebellum.

6.1.3. Tertiary Endpoints

- Correlation between spinal cord volume (total and GM, WM separately) and several brain metrics (total brain volume, GM, WM, lateral ventricles, thalamus, corpus callosum, brainstem and cerebellum) in HC.
- Description of results from different MRI protocols (shorter and longer version, different sequences)

6.2. Demography and Baseline Clinical Characteristics

Demographics and baseline data will be reported with summary statistics (mean and standard deviation [SD], median and range)

6.2.1. Analysis Population

The analysis population will be all participants with all available clinical and MRI data uploaded into the database.

6.2.2. General Methods of Analysis

In general, continuous variables will be presented with summary statistics (mean, SD, median, range) and a 95% confidence interval (CI), and categorical variables will be presented with frequency distributions.

6.2.3. Primary Endpoint Analysis

Establishing pathological cut-offs for spinal cord volume able to discriminate with the highest sensitivity and specificity HC from MS patients will be done by employing cross-sectional and longitudinal logistic regression model and ROC analysis. The cross-sectional analysis will be done at each timepoint. Moreover, the pairwise comparison of results between each pair of timepoints will be done in order to analyse the robustness (stability) of results. Longitudinal analysis will be done to identify cut-offs of changes of spinal cord volume over 3 years follow-up.

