- Description of results of different normalisation strategies, using different variables, e.g. sex, age, body height, height of C3 vertebra (or other vertebra

derived metrics), total intracranial volume (TIV).

- Description of absolute and normalised spinal cord volume and its variability in predefined spinal segments in different age and sex groups of HC.
- Description of absolute and normalised brain volumes in HC measuring whole brain, TIV and different regional brain volumes, especially – gray and white matter compartment, corpus callosum, thalamus, and cerebellum.

Tertiary Endpoints

- Correlation between spinal cord volume (total and GM, WM separately) and several brain metrics (total brain volume, GM, WM, lateral ventricles, thalamus, corpus callosum, brainstem and cerebellum) in HC.
- Comparison of results from different MRI protocols

Study Design:	Prospective, longitudinal, monocentric, interventional study
Study Location:	Czech Republic
Number of Planned Subjects:	102 subjects – intended as healthy controls (HC) from general population
Study Population:	This study is conducted in healthy subjects. Detailed criteria are described in the protocol.
Statistical Methods:	Binary or categorical variables will be presented as frequency distributions. Continuous variables will be reported by summary statistics: mean and standard deviation (SD) or median and range. The relationship between age and spinal cord volume will be determined separately for female and male patients in different decades to determine sex- and age-related effects on spinal cord volume. The spinal cord volume (and eventually also spinal cord gray- and white matter volumes) will be compared in three age-specific groups: 18-30 years, 30-40 years and 40-60

CONFIDENTIAL

years.

Annualised change of spinal cord volume will be calculated for each participant as the slope of a regression line fitted to all four timepoints (M0, 12, 24 and 36) with the assumption of linear change over time for each participant and for all participant (in a decade-specific manner) together.

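### The primary cut-off has no stated selection rule and no internal validation; if it is the empirical ROC maximum, its sensitivity and specificity will be overstated by roughly 2 to 4 points each (102 v 102).

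*Combined protocol and SAP*

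**What the plan says.** The primary endpoint (section 2.3.1, repeated in 6.1.1) is "Establishing pathological cut-offs for spinal cord volume able to discriminate with the highest sensitivity and specificity HC from MS patients". Section 6.2.3 gives the method: the search for the cut-off that separates "with the highest sensitivity and specificity HC from MS patients will be done by employing cross-sectional and longitudinal logistic regression model and ROC analysis". No rule for picking the point on the ROC curve is given.

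Section 6.2.1 forms one undivided data set: "The analysis population will be all participants with all available clinical and MRI data uploaded into the database". The documents mention no cross-validation, bootstrap, hold-out sample or external cohort.

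The one planned check is in 6.2.3: "the pairwise comparison of results between each pair of timepoints will be done in order to analyse the robustness (stability) of results". Those timepoints come from the same HC, because "each participant will be examined by MRI at month 0, 12, 24, and 36" (section 3.2).

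A second cut-off, for change, is planned in the same section: "Longitudinal analysis will be done to identify cut-offs of changes of spinal cord volume over 3 years follow-up". The Synopsis defines individual change: "Annualised change of spinal cord volume will be calculated for each participant as the slope of a regression line fitted to all four timepoints". Separately, a secondary objective (2.2.2) is to "choose the best variable or set of variables to normalize spinal cord volume".

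**The concern.** A cut-off chosen because it maximises accuracy in a sample fits the chance features of that sample. Sensitivity and specificity read from the same people then exceed what the cut-off will achieve in new people. Asking for the highest sensitivity and specificity by ROC analysis is naturally read as taking the empirical maximum, and nothing in the plan rules that out.

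The cut-off is the primary endpoint, and these two figures are the obvious measure of its worth. If specificity is overstated, more healthy people will be called pathological than the report says. An ordinary confidence interval that ignores the choice of cut-off will also be centred too high and will cover the true value too rarely.

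**Working it through.** **Plan's own figure.** Section 6.3.2 sets at least 10 per age and sex cell, a 1:2 male to female ratio and 2 extra per cell for dropout. With 20 women per cell inferred from the ratio: 3 × (10 + 2) + 3 × (20 + 2) = 36 + 66 = 102, which agrees with Table 1. Losing the allowance leaves 102 − 6 × 2 = 90.

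**Inputs the documents do not give.** These are the number of MS patients, the separation between groups, the SD and the cut-off rule. Assumed: normal volumes with equal SD; AUC 0.60 to 0.90; 102 MS patients (1:1) or 1,036 (the MS cohort already measured with this software, section 2, used only as an upper end).

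**Model.** In SD units, HC ~ N(0, 1) and MS ~ N(−d, 1), so AUC = Φ(d/√2). AUC 0.60 gives d = √2 × 0.253 = 0.36, and AUC 0.90 gives d = √2 × 1.282 = 1.81. Gaps of 0.5 and 0.8 SD correspond to AUC 0.64 and 0.71. A cut-off c has true sensitivity Φ(c + d) and true specificity 1 − Φ(c). Optimism is the apparent minus the true value for the same c.

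**Empirical Youden maximum, mean optimism in points (simulation, sensitivity / specificity).**

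| AUC | 102 v 102 | 90 v 90 | 102 HC v 1,036 MS |
|---|---|---|---|
| 0.60 | 3.7 / 3.7 | 3.9 / 3.9 | 0.4 / 4.7 |
| 0.70 | 3.0 / 3.2 | 3.4 / 3.3 | 0.4 / 4.0 |
| 0.80 | 2.5 / 2.6 | 2.9 / 2.8 | 0.3 / 3.4 |
| 0.90 | 2.2 / 2.2 | 2.3 / 2.3 | 0.3 / 2.8 |

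These are averages. At 102 v 102 the apparent sum of the two measures exceeded the true sum in about 82% to 92% of runs.

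**Relative to sampling error.** The best true specificity is Φ(d/2), with standard error √(p(1 − p)/102).
- AUC 0.60: p = 0.571, SE = 4.9 points, 3.7/4.9 = 0.76.
- AUC 0.90: p = 0.818, SE = 3.8 points, 2.2/3.8 = 0.58.

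The bias is thus about 0.6 to 0.8 of one standard error. An ordinary 95% CI for specificity covers the true value about 90% to 93% of the time at 102 v 102, and about 87% to 92% with 1,036 MS patients.

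**Other rules, 102 v 102.** The closest-to-corner rule gives 1.7 to 2.4 points each. A model-based midpoint gives at most 0.2 each. A logistic cut-off at fitted probability equal to the MS share gives at most 0.3 in total.

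**The cut-off itself.** At 102 v 102 its mean is within a few hundredths of an SD of the ideal value. Its sampling SD is about 0.4 SD at a gap of 0.5 and 0.3 SD at a gap of 0.8, which is 0.4/0.5 = 80% and 0.3/0.8 = 38% of the whole gap between groups. The loss in true accuracy is small. At a gap of 0.5 the best possible sensitivity + specificity − 1 is 2Φ(0.25) − 1 = 0.197, and the chosen cut-off attains 0.183 (apparent 0.250). At 0.8 the figures are 0.311, 0.297 and 0.358.

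**Does the timepoint comparison reveal the optimism?** Taking gaps of 0.5 and 0.8, 102 v 102 and between-visit correlations of 0.80 to 0.98:
- Re-derived at each visit: the mean difference between visits is at most 0.0015, although each visit is overstated by 0.059 to 0.070 in the sum. The optimism cancels.
- Month 0 cut-off carried forward: 56% to 90% of the optimism shows if MS patients are re-scanned, and 27% to 45% if they are not.

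**Does resampling work?** At 102 v 102, repeated 10-fold cross-validation gives apparent / corrected / true values of 0.254 / 0.186 / 0.184 (gap 0.5) and 0.357 / 0.297 / 0.297 (gap 0.8) for sensitivity + specificity − 1. Plain bootstrap correction leaves 24% to 31% of the optimism.

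**The case against.** The strongest reply is that the size rests on choices the plan has not made. Section 6.2.3 names logistic regression as well as ROC analysis, and a cut-off from the fitted model would have almost no optimism. That stands, so the figure must stay conditional. It does not remove the concern, because the text leaves the optimistic rule open and points towards it.

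Second, the endpoint is the cut-off, not its accuracy, and the cut-off is nearly unbiased. That also stands. A reader might infer that the threshold itself will be shifted; neither the plan nor the working supports that. The problem with the threshold is imprecision, and 6.2.3 plans nothing specific to express it, beyond a general 95% CI for continuous variables in 6.2.2.

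Third, the bias is under one standard error at 102 v 102. True, but it runs upward on average and it is cheap to remove.

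Fourth, the timepoint comparison is a real check. It can expose an unstable cut-off, and a cut-off carried forward would show part or even most of the optimism. But the cross-sectional analysis at each timepoint reads more naturally as re-derivation, and then the optimism cancels.

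**Conclusion.** The concern holds in conditional form. No cut-off rule is stated, and no validation is planned in people who did not set the cut-off. If the empirical Youden maximum is used with 102 v 102, sensitivity and specificity are overstated on average by roughly 2 to 4 points each. With a much larger MS group the excess is about 3 to 5 points, nearly all on specificity. Normality, equal SDs, AUC 0.60 to 0.90 and both MS group sizes are assumptions. The omission is certain; the size is not. It should be corrected before analysis, but it does not invalidate the study.

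Four stronger readings are not supported:
- That the reported figures will certainly be inflated: this depends on a rule the plan does not state.
- That the 1,036 MS patients are the comparator: no section says so.
- That a numerical excess can be attached to the 3-year-change cut-off. The same gap exists there, but section 6.3.2 gives only a 3 to 5 fold ratio of loss, with no HC rate or SD, and no MS follow-up is described.
- That choosing the normaliser adds a known amount. A data-driven normaliser used in the cut-off would add optimism, but no section says that it enters the primary cut-off or how it would be selected.

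**What to change.** In section 6.2.3:

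1. Name the cut-off rule, and state the number and source of the MS patients.
2. For the cross-sectional and the 3-year-change cut-offs, report apparent and optimism-corrected sensitivity and specificity. Use participant-level resampling that repeats every data-driven step (normaliser if used, model, cut-off) and keeps all visits of a person together. Repeated 10-fold cross-validation is suitable; plain bootstrap correction removed too little of the bias above.
3. Give each cut-off a participant-level bootstrap 95% CI, and give the corrected sensitivity and specificity 95% CIs whose resampling repeats the cut-off choice.
4. Keep the timepoint comparison, described as stability over time, and say whether the cut-off is re-derived at each visit or carried forward from month 0.

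The cost is a few lines of SAP text and a little computing, with no new scans or participants. Reported accuracy will be slightly less favourable, or almost unchanged if a model-based cut-off is chosen.

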6.3.2. Sample Size Calculation

The exact sample size calculation is difficult due to several problems – there is very limited data about spinal cord volume in both MS patients and HC. In addition to that spinal cord volume is scanner and protocol specific, so it is not possible to use directly data from other centres.

Based on current knowledge we can estimate that MS patients are losing spinal cord volume 3-5 times faster compare to HC. The problem is that this can be age and sex specific and different in different MS phenotypes. So, it is reasonable to choose the group of HC that the best copy a typical MS patient population, i.e. ratio of male : female 1:2 and age range 18-60 years.

From the statistical point of view is generally recommended to have at least 10 subjects in each age and sex specific subgroup (see Table 1). Taking into account that the study is planned for 4 years and there is a risk of drop out of some participants we recommend to increase number of participants in each group by 2.

Based on this conditions we recommend to enrol:

Table 1.

Age range / Sex	Male	Female
18-30 years	12	22
30-40 years	12	22
40-60 years	12	22
Total	36	66

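### Section 6.2.3 judges robustness by comparing HC-versus-MS results between visits, but the plan's own atrophy premise says those results should change if MS patients are re-scanned

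*Combined protocol and SAP*

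**What the plan says.** Section 6.2.3 (Primary Endpoint Analysis) uses logistic regression and ROC analysis to find cut-offs that separate HC from MS. It states: "The cross-sectional analysis will be done at each timepoint". It then adds that "the pairwise comparison of results between each pair of timepoints will be done in order to analyse the robustness (stability) of results". A separate sentence covers change: "Longitudinal analysis will be done to identify cut-offs of changes of spinal cord volume over 3 years follow-up".

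Section 6.3.2 gives the expected natural course: "we can estimate that MS patients are losing spinal cord volume 3-5 times faster compare to HC". It qualifies this at once, saying that "this can be age and sex specific and different in different MS phenotypes".

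Section 3.2 sets the visits: "each participant will be examined by MRI at month 0, 12, 24, and 36". Section 3.2.2 repeats this. Participants in this study are healthy controls. Section 2.2.1 describes the MS comparator only as matched on age and sex; its size, source and scan schedule are not given. The Introduction mentions 1,036 MS patients measured in 2016-2017 but does not say that they are the comparator.

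**The concern.** A stability check needs a target that should stay constant. Visits a year apart are not replicates: controls are 3 years older at M36, and on the plan's premise MS patients have lost several times more cord over the same period. If both groups are followed, a valid method should give different AUCs, sensitivities and optimal cut-offs at M0 and M36.

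The check can mislead in two ways. Real atrophy could be reported as an unstable method. Agreement across visits could be reported as robustness when the premise predicts change. Section 6.2.3 names no expected change, tolerance or test, and does not say which result is compared. The robustness statement attached to the primary endpoint would therefore rest on judgement made after the data are seen.

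**Working it through.** **The plan's own figure.** Section 6.3.2 takes at least 10 per age-sex cell, a male:female ratio of 1:2 and 2 extra per cell: 3 × [(10+2) + (20+2)] = 3 × 34 = 102. This reproduces exactly. It is a cell-count rule, so it supplies no loss rate, SD or tolerance for what follows.

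**Inputs.** From the documents: ratio of MS to HC loss k = 3 to 5 (6.3.2), and 3 years of follow-up (3.2). Assumed, because the documents do not state them: HC loss r = 0.2-0.3% of mean volume per year; between-subject SD s = 8-10% of the mean, equal in both groups; baseline gap 0.5 SD; normal distributions; MS patients re-scanned in step with HC.

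**Formulas.**
- Youden cut-off = midpoint of the two means. Its 3-year fall = 3r(1+k)/2.
- Growth in separation = 3r(k−1).
- AUC = Φ(d/√2), with d the gap in SD units.
- With the M0 cut-off kept: HC specificity = Φ(0.25 − 3r/s) and MS sensitivity = Φ(0.25 + 3rk/s).

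**Results, M0 to M36, with no measurement problem.**

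| | M0 | r=0.2, k=3, s=10 | r=0.3, k=5, s=8 |
|---|---|---|---|
| Fall in Youden cut-off | – | 3×0.2×4/2 = 1.2% (0.12 SD) | 3×0.3×6/2 = 2.7% (0.34 SD) |
| AUC | Φ(0.5/√2) = 0.64 | Φ(0.62/√2) = 0.67 | Φ(0.95/√2) = 0.75 |
| Specificity, M0 cut-off kept | Φ(0.25) = 60% | Φ(0.19) = 58% | Φ(0.1375) = 55% |
| Sensitivity, M0 cut-off kept | 60% | Φ(0.43) = 67% | Φ(0.8125) = 79% |

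**How far this depends on the assumptions.**
- *HC ageing removed from the volumes.* The cut-off still falls by 3r(k−1)/2, which is 0.9-1.8% at r = 0.3.
- *MS set fixed, not re-scanned.* The ratio drops out. Only HC ageing acts, and the cut-off falls by 3r/2 = 0.45% at r = 0.3. With s = 10, AUC falls slightly, to Φ((0.5−0.09)/√2) = 0.61.
- *MS volumes more variable* (SD 12-14% against 10%) *with a 3% gap.* At r = 0.3 the Youden cut-off moves by only −0.21% to +0.19%. AUC = Φ(gap/√(SD₁²+SD₂²)) still rises from 0.57-0.58 to 0.61-0.66, as the gap grows from 3% to 4.8% (k = 3) or 6.6% (k = 5).

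**Sampling noise** (simulation, 102 HC and 102 MS, SD 10%, gap 5%). The M0-to-M36 change in a re-derived empirical Youden cut-off has an SD of about 3.6-4.1 points, against a drift of 1.8-2.7 points at r = 0.3. With no true change at all, the cut-off still falls by more than 1 point in 34% of runs. The paired change in AUC is much more precise: it rises by 0.05-0.09 with an SD of about 0.01.

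**The case against.** The strongest reply has four parts.

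1. *The ratio alone gives no size.* This stands. Without an absolute loss rate, 3-5 times faster cannot be turned into a drift, and section 6.3.2 itself allows the ratio to vary by age, sex and phenotype. A reader might infer that a correct cut-off must drift. The documents do not support that: the drift can be near zero with unequal SDs.

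2. *Re-scanning of MS patients is not stated.* This also stands, because the M0-M36 schedule is written for controls. The planned cut-offs for change over 3 years, within an endpoint that separates HC from MS, do suggest serial MS data, but they do not establish it.

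3. *The plan does not say that a difference means failure.* Correct. A reader might infer that a shift would be read as instability. Section 6.2.3 has no such rule and leaves the compared result undefined, so the most that can be said is that it could be. The change analysis in the same section, and the annual slopes in the synopsis, would help to interpret a shift, but neither is linked to the stability comparison. Age as a normalisation variable would remove only the HC-ageing part.

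4. *Noise exceeds drift for a re-derived cut-off.* True, but this does not rescue the check. A comparison that often moves with no true change cannot demonstrate stability, and for AUC the expected change would be plainly visible.

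**Conclusion.** The concern holds in conditional form. The analysis does not match its stated purpose: if MS patients are re-scanned alongside controls, the plan's own premise predicts changing results, so agreement between visits is not what a valid method should show. Under the stated assumptions AUC rises from 0.64 to 0.67-0.75 and the Youden cut-off falls 1.2-2.7% over 3 years. The AUC change persists when MS volumes are more variable; the cut-off drift may not. With a fixed MS set the cut-off drift is about 0.45% at 0.3%/year.

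Only the ratio and the follow-up time come from the documents; every other input is an assumption. The cut-offs themselves can still be estimated. What cannot be relied on as written is the statement about their robustness.

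**What to change.** In section 6.2.3, stop using agreement of re-derived results across visits as the robustness test. Instead:

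- Derive the cut-off at M0 and correct its apparent sensitivity and specificity for optimism by bootstrap. In simulation the apparent M0 specificity was 64% against a true 60%. Then freeze the cut-off and apply it unchanged at M12, M24 and M36.
- Report the raw change in HC specificity with a 95% CI that respects repeated measures on the same people. Its SD is about 2 points with 102 controls and no artefact.
- Report changes in MS sensitivity and AUC as disease course, not as instability. State whether and when MS patients are re-scanned, since these figures depend on it.
- Do not benchmark HC specificity against a path estimated from the same controls' slope. Steady scanner drift would be absorbed into that slope. In simulation, artefactual loss of 1-2%/year cut specificity by 17-28 points yet left a mean departure from the fitted path of about 0.1 point.
- State that HC ageing and steady scanner drift cannot be told apart from these data alone.

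Cost: SAP wording, a bootstrap and a few table rows, with no new HC data. The downside is some extra analysis and a less favourable, optimism-corrected accuracy at M0.
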